6.2.3 Follow-up period and trial completion

Every effort should be made for all patients who complete the total 48-week treatment period or who discontinue the trial early, to return for a Safety Follow-up Visit 10 weeks after last dose of trial medication (at Week 56 for patients who complete the full treatment period).

Safety follow-up visit

The following will be performed/collected:

- Physical examination, including weight (kg) (see Section 5.3.1)
- Vital signs (blood pressure, pulse rate, and body temperature; see Section 5.3.2)
- Laboratory testing (serum chemistry, hematology, and urinalysis; see Section 5.3.3)
- Urine pregnancy test for women of childbearing potential
- 12-lead ECG (see Section 5.3.4)
- Previous and concomitant therapy (see Section 4.2)
- Assessment of AEs (see Section 5.3.6)

Page 61 of 93

Proprietary confidential information © 2017 Boehringer Ingelheim International GmbH or one or more of its affiliated companies

• End of participation

Unscheduled visit assessments

Patients may attend the trial site for unscheduled visits at any time for additional safety monitoring at the discretion of the investigator.

Page 62 of 93

Proprietary confidential information © 2017 Boehringer Ingelheim International GmbH or one or more of its affiliated companies

7. STATISTICAL METHODS AND DETERMINATION OF SAMPLE SIZE

7.1 STATISTICAL DESIGN - MODEL

This is a randomized, double-blind, parallel arm, multiple dose, multicenter, multinational, active comparator trial of BI 695501 and EU-approved Humira.

The primary objective of this trial is to compare the clinical efficacy of BI 695501 with EU-approved Humira in patients with active CD at the end of the induction phase at Week 4 by means of the RR.

The primary endpoint (Section 5.1.1) will be analyzed using a log-linked binomial model, which will include stratification factors as covariates (i.e., prior exposure to infliximab [yes/no] and screening SES-CD (<16 or \geq 16).

7.2 NULL AND ALTERNATIVE HYPOTHESES

This exploratory trial is intended to generate additional data in patients with active CD. Therefore, no formal confirmatory hypotheses for the primary efficacy analysis are defined.

7.3 PLANNED ANALYSES

The primary analysis set will be the FAS according to the intention to treat principle. The FAS will consist of all randomized patients who receive at least one dose of trial medication, and have all efficacy measures relevant for the CDAI, measured at baseline and at least once post-baseline.

A PPS of patients who have followed the CTP in all essential criteria will be created for sensitivity analyses. Patients included in the FAS who have important protocol violations relevant for efficacy prior or at Week 4 will be excluded from the PPS. Protocol violations will be assessed on a case-by-case basis. A protocol violation will be considered important if it can be expected to have a distorting influence on the assessment of the primary endpoint. Important protocol violations may include:

- Incorrect trial medication taken until Week 4
- Violation of treatment compliance until Week 4
- Violation of inclusion/exclusion criteria
- Further details on the definition of the different analysis sets will be provided in the TSAP.

All patients treated with at least one (full or partial) dose of either of the trial treatments during any dosing period will be included in the safety evaluation (SAF).

7.3.1 Primary endpoint analyses

Primary efficacy analysis:

The primary analyses will be performed on the FAS. Patients will be assigned to the treatment they were randomized to receive.

The primary analysis of the observed proportion of patients with a clinical response (CDAI decrease of \geq 70 compared with baseline) at Week 4 will be based on log-linked binomial model. No missing data imputation for primary analysis endpoint need to be taken into account due to FAS definition. However, for pre-specified criteria non-responder imputation (NRI) will be applied (see Section 7.5).

The statistical model can be described as follows:

• (M1) Response to treatment at Week 4 = treatment + prior infliximab exposure + screening SES-CD

This model includes the stratification factor, prior exposure to infliximab, and treatment as fixed, categorical effects and it will be investigated whether the baseline SES-CD will be included as a continuous or as a categorical effect:

- Treatment (BI 695501, EU-approved Humira)
- Prior exposure to infliximab (Yes/No)
- Baseline SES-CD ($<16 \text{ or } \ge 16$)

The relative risk estimate together with its 90% and 95% CI (ratio scale) will be produced.

Further efficacy analyses:

As sensitivity analyses to the primary analysis, the primary endpoint will also be analyzed on the PPS with NRI.

The following explorative hypotheses are not intended to support any biosimilarity claim for BI 695501; however, the framework of non-inferiority testing will be used to compare efficacy of BI 695501 versus EU-approved Humira in a descriptive way.

The following hypotheses will be investigated:

- H_0 : RR of proportion of patients with a clinical response (CDAI decrease of \geq 70 compared with baseline) at Week 4 (BI 695501 versus EU-approved Humira) is less than or equal to 0.76
- H₁: RR of proportion of patients with a clinical response (CDAI decrease of ≥70 compared with baseline) at Week 4 (BI 695501 versus EU-approved Humira) is greater than 0.76

Two-sided 90% CI will be used for the comparison.

The applied margin (0.76 on the ratio scale for CDAI 70) does preserve 39% of the historical effect of adalimumab over placebo (based on a meta-analysis of GAIN and CLASSIC1; see Appendix 10.3 for further details).

7.3.2 Secondary endpoint analyses

7.3.2.1 Secondary efficacy endpoints

To support the primary objective, the secondary efficacy endpoints detailed in Section 5.1.2 will be analyzed descriptively based on the FAS.

For the proportions, the risk difference will be computed and presented together with its 90% and 95% CI and interpreted in a descriptive manner.

7.3.2.2 Secondary safety endpoints

The secondary safety endpoints detailed in Section 5.1.2 will be based on the SAF and presented descriptively. In addition, RR and risk difference together with 95% CIs will be presented.

7.3.4 Safety analyses

Adverse events will be coded using the MedDRA coding dictionary.

Boehringer Ingelheim		12 Dec 2017
BI Trial No.: 1297.4		
c09542349-05	Trial Protocol	Page 65 of 93

All treated patients will be included in the safety analysis. In general, safety analyses will be descriptive in nature. No hypothesis testing is planned. No formal inferential analyses are planned for safety comparison. The analyses will be based on the SAF.

Statistical analysis and reporting of AEs will concentrate on treatment-emergent AEs. To this end, all AEs occurring between start of treatment and end of the REP will be considered 'treatment-emergent'. The REP is defined as 10 weeks after the last dose of trial medication. Adverse events that start before first drug intake and deteriorate under treatment will also be considered as 'treatment-emergent'. Other AEs will be assigned to the appropriate trial phases, i.e., screening or post-treatment. For patients switching from EU-approved Humira to BI 695501, AEs occurring after the first dose of BI 695501 will be assigned to BI 695501 for the overall AE analysis. AEs occurring before the first dose of BI 695501 will be assigned to the ongoing treatment.

Frequency, severity, and causal relationship of AEs will be tabulated by system organ class and preferred term after coding according to the current version of MedDRA. In addition, RR and risk difference together with 95% CIs will be presented for the overall population (details will be specified in the TSAP).

Laboratory data will be analyzed quantitatively as well as qualitatively. The latter will be done via comparison of laboratory data with their reference ranges. Values outside the reference range as well as values defined as clinically relevant will be highlighted in the listings. Treatment groups will be compared descriptively with regard to distribution parameters as well as with regard to frequency and percentage of patients with abnormal values or clinically relevant abnormal values.

Vital signs, physical examinations, or other safety-relevant data observed at screening, baseline, during the course of the trial and at the end-of-trial evaluation will be assessed with regard to possible changes compared with findings before start of treatment.

Page 66 of 93

Proprietary confidential information © 2017 Boehringer Ingelheim International GmbH or one or more of its affiliated companies

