3.3. CHANGES TO ANALYSIS FROM PROTOCOL

No change to analysis from protocol is planned.

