16.1.1. ADVERSE EVENT SPECIFIC DERIVATION

16.1.1.1. Treatment Emergent Adverse Event

Treatment-Emergent Adverse Events (TEAEs) are defined as AEs that started or worsened on or after the first dose of trial medication and prior to the last date of trial medication + 10 weeks (70 days) inclusive.

There are two specific periods of interest:

Period 1 Treatment-Emergent Adverse Events (P1 TEAEs) are defined as AEs that started or worsened on or after the first dose of trial medication and prior to the date of Week 24 visit or within 10 weeks (70 days, inclusive) after the last dose of IMP for patients who discontinued the treatment before Week 24.

Period 2 Treatment-Emergent Adverse Events (P2 TEAEs) are defined as AEs that started or worsened on Week 24 visit and prior to or on the Week 56 visit or within 10 weeks (70 days, inclusive) after the last dose of IMP for patients discontinuing treatment prior to Week 46.

Non-TEAEs will be classified as "Screening" if AE start date is strictly prior to the first injection date. Non-TEAEs will be classified as "Post treatment" if AE start date is strictly after the last injection date + 70 days.

See APPENDIX 2 for handling of partial dates for AEs. In the case where it is not possible to define an AE as treatment-emergent or not, the AE will be classified by the worst case, i.e., treatment-emergent in the period of the last injection of trial medication.

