16.1.1.2. Risk ratio

Risk ratios and associated 95% exact confidence interval will be presented for all adverse events.

Risk ratio will be defined as: $[a/(a+b)]/[c/(c+d)]$

where:

- **a** is the number of subjects with AE within treatment group BI 695501
- **a+b** is the total number of subjects in treatment group BI 695501
- **c** is the number of subjects with AE within treatment Humira
- **c+d** is the total number of subjects in treatment group Humira

PROC FREQ with option RELRISK will be used for programming purpose.

```
proc freq data=data;  
  tables trt*ae_overall;  
  exact relrisk(method=score);  
  weight count;
```

run;

Document: \\ieedc-
vnasc01\BIOSdata\Boehringer_Ingelheim\BI_695501\NVA96252\Biostatistics\Documentation\S
AP\BI1297.4 SAP FINAL v4.0_22MAY2019.docx

Author: Version Number: Final V4.0
Version Date: 22MAY2019

Template No: CS_TP_BS016 Revision 5
Effective Date: 01Apr2018

Reference: CS_WI_BS005

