16.1.2. ALL TEAEs

Number of subjects, percentages, and number of events overall and for period 1 and period 2 will be presented by SOC and PT and also broken down further by maximum intensity and relationship to trial medication.

Periods for TEAE's:

Period 1	Visit date within 
 • [first injection date; Week 24 Visit] or • [first injection date; last injection date + 10 weeks (70 days)] (for patients that discontinued the treatment before week 24)].
Period 2	Visit date within 
 • [Week 24 Visit; Week 56 Visit[or • [Week 24 visit; last injection date + 10 weeks (70 days)] (for patients that discontinued the treatment before week 56)].

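### The protocol's rule for switchers makes the overall adverse-event risk ratio compare unequal observation time, and no risk ratio is expressly tied to the pre-switch period

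*Protocol*

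**What the plan says.** Protocol 7.3.4 attributes events in patients who switch from Humira to the product being taken. Before the switch they belong to Humira; afterwards, "AEs occurring after the first dose of BI 695501 will be assigned to BI 695501 for the overall AE analysis". The next paragraph says that "RR and risk difference together with 95% CIs will be presented for the overall population" and leaves the details to the SAP. Protocol 7.3.2.2 plans the same two measures for the secondary safety endpoints.

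SAP 3.3 states: "No change to analysis from protocol is planned". SAP 16.1.1.2 states: "Risk ratios and associated 95% exact confidence interval will be presented for all adverse events". Its formula is [a/(a+b)]/[c/(c+d)], where a+b "is the total number of subjects in treatment group BI 695501", and its code uses an overall adverse-event flag. SAP 16.1.1.3 takes the risk difference from the same code. Neither section has a term for time at risk, names a period, or says how switchers enter the numerators and denominators.

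The SAP does split the trial at the switch. SAP 16.1.1.1 says: "Period 1 Treatment-Emergent Adverse Events (P1 TEAEs) are defined as AEs that started or worsened on or after the first dose of trial medication", with an end before the Week 24 visit, or 70 days after the last dose for patients who stop earlier. SAP 16.1.2 plans "Number of subjects, percentages, and number of events overall and for period 1 and period 2". It names no risk ratio or risk difference for either period.

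**The concern.** Under the protocol rule the two columns of the overall table differ in length of observation as well as in product. Humira stops collecting events from its responders at about Week 24. BI 695501 collects them to Week 56 and also receives the post-switch time of the Humira arm. A crude proportion grows with the window, so two identical products would not be expected to give a risk ratio of 1. If switchers also join the BI 695501 denominator, the same patient sits in both groups while the confidence interval treats the groups as independent.

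Comparing safety is a secondary objective (Protocol 2.2), and a risk ratio with a confidence interval is the figure most readers will take as the product comparison. They could not correct it by eye, because the direction of the bias depends on when events occur and on an unstated denominator.

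**Working it through.** **Inputs from the documents**
- 1:1 allocation, 65 per arm (Protocol 7.7).
- Week 4 non-responders stop treatment (Protocol 4.1.4). Flow Chart A puts their safety follow-up at Week 14.
- Humira responders switch at Week 24 (Protocol 3.1).
- The last dose is at Week 46 and events count for 10 more weeks: 46 + 10 = 56. Day 56 × 7 + 1 = 393, which agrees with Flow Chart B.
- Response rate r: 0.80 (Protocol 7.7) or 0.54 (pooled historical 54.1%, Protocol Appendix 10.3).

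**Assumptions.** The plan states no adverse-event rate, so none can be reproduced. I let the 24-week risk q run from 5% to 50%, with 80% and 95% as extremes. Both products have the same constant hazard, and nobody drops out except at Week 4. An event after the switch counts for BI 695501 whether or not that patient had one on Humira.

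**Step 1: windows.** Responders are counted for 56 weeks (BI 695501) and 24 weeks (Humira). Each switcher adds 56 − 24 = 32 weeks to BI 695501. At r = 0.80, the mean window per counted subject is:
- BI 695501 with switchers in the denominator: (0.8×56 + 0.2×14 + 0.8×32)/1.8 = 73.2/1.8 = 40.7 weeks
- Humira: 0.8×24 + 0.2×14 = 22.0 weeks

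**Step 2: formulas.** λ = −ln(1−q)/24 and P(w) = 1 − exp(−λw).
- BI 695501 arm: B = r·P(56) + (1−r)·P(14)
- Humira arm: H = r·P(24) + (1−r)·P(14)
- Switchers after Week 24: S = P(32)
- (a) Switchers in the BI 695501 group: RR = [(B + r·S)/(1+r)]/H
- (b) Switchers' later events left out: RR = B/H

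**Step 3: example, q = 20%, r = 0.80.** P(14) = 0.122, P(24) = 0.200, P(32) = 0.257, P(56) = 0.406.
- B = 0.8×0.406 + 0.2×0.122 = 0.349; H = 0.8×0.200 + 0.2×0.122 = 0.184
- BI 695501: 65×0.349 + 52×0.257 = 36.1 of 117, or 30.8%
- Humira: 65×0.184 = 12.0 of 65, or 18.4%
- RR (a) = 1.67, difference 12.4 points; RR (b) = 0.349/0.184 = 1.89

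**Step 4: range, identical products**

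| 24-week risk | (a) r=0.54 | (b) r=0.54 | (a) r=0.80 | (b) r=0.80 |
|---|---|---|---|---|
| 5% | 1.76 | 1.84 | 1.80 | 2.09 |
| 20% | 1.64 | 1.68 | 1.67 | 1.89 |
| 50% | 1.40 | 1.39 | 1.42 | 1.52 |
| 80% | 1.17 | 1.13 | 1.17 | 1.19 |
| 95% | 1.05 | 1.03 | 1.05 | 1.04 |

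Ending non-responder windows at Week 12 (Week 2 dose plus 10 weeks) instead of Week 14 moves these by at most 0.06. If switchers' events were added but the denominator stayed at 65, the Step 3 example would give (0.349 + 0.8×0.257)/0.184 = 3.01.

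**Step 5: early events.** Multiply the hazard after Week 8 by 0.1 or by 0 and rescale to the same 24-week risk (5-50%). With switchers in the denominator, the RR is 0.83-0.89 and 0.56-0.65 respectively. Switchers then add subjects but few or no events.

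**Step 6: randomised-group reading.** Suppose switchers stay under Humira to Week 56. Identical products give RR 1.00. For a true hazard ratio of 2, BI 695501 uses 2λ throughout, and overall Humira risk is r·[1 − exp(−(24 + 2×32)λ)] + (1−r)·P(14). With q = 5-20% and r = 0.80, the RR is 1.81-1.95 in Period 1 but 1.20-1.27 overall (overall 1.27-1.33 at r = 0.54).

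**Step 7: Period 1.** Both arms have 24 weeks for responders and the same window for non-responders, so identical products give an expected RR of 1.00.

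**The case against.** The strongest reply is that the SAP does not adopt the reassignment rule. In the protocol, the rule and the risk-ratio sentence are separate. The overall population may mean all patients rather than the whole trial period, and the details were delegated to the SAP. The SAP formula has two groups in which a subject would naturally be counted once, so identical products would give 1.00. This reading is possible. But it conflicts with the protocol rule while SAP 3.3 declares no change, it counts events on BI 695501 as Humira events, and Step 6 shows that it dilutes a real difference.

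Second, SAP 16 opens by saying that safety outputs are for overall and period, which could cover a Period 1 risk ratio, and the table templates mentioned in SAP 8 are not available to us. Both points limit the claim to this: no visible text expressly ties a risk ratio to Period 1. Neither repairs the overall ratio.

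Third, SAP 4.1 cuts safety data for the primary analysis at the Week 4 visit, so a ratio produced there compares equal time. That is true, but it covers only four weeks.

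Fourth, attribution to the product being taken is a recognised convention, safety is descriptive, the trial is exploratory, and Period 1 percentages will be available. These points keep the matter below a threat to the trial's conclusions. They do not justify publishing a between-product ratio that mixes product with time.

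**Conclusion.** The concern holds: the rule as written gives a misleading comparison. Unequal time follows from the Week 24 switch and follow-up to Week 56, and needs no assumption about event rates. It affects responders; Week 4 non-responders have equal windows in both arms.

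The size does depend on assumptions. Identical products give an expected ratio of about 1.4 to 2.1 with a constant hazard and a 24-week risk of 5-50%, close to 1 for very common events, and below 1 if events cluster early and switchers are in the denominator. The alternative randomised-group reading is unbiased for identical products but pulls a true hazard ratio of 2 down to a risk ratio of about 1.2 to 1.3. No test or decision uses the ratio, so the harm is to interpretation. It should be corrected before the final analysis.

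**What to change.** 1. In SAP 16.1.1.2 and 16.1.1.3, base every BI 695501 versus Humira adverse-event risk ratio and risk difference, with its CI, on Period 1 treatment-emergent events.
2. Present Period 2 and overall events by sequence (BI 695501 throughout; Humira then BI 695501), with exposure-adjusted rates and no between-product risk ratio or risk difference.
3. Do not apply the reassignment rule in any table that carries a risk ratio or risk difference. In any table that keeps the rule, state whether switchers are in the BI 695501 denominator.
4. Declare this in SAP 3.3 as a departure from Protocol 7.3.4, or amend the protocol.

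The cost is SAP wording, revised table shells and the loss of the overall risk-ratio columns. No new data are needed, because the SAP already derives Period 1.

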7.4 INTERIM ANALYSES

No classic interim analysis will be performed. Instead, an overview of the different analysis time points is given below.

7.4.1 Primary analysis

The primary analysis will take place when all primary efficacy endpoint data are available and cleaned (i.e., approximately 4 weeks after the last patient has been randomized). The cut-off date will be the date on which the last patient completes the Week 4 visit and will be the same for all patients. A database snapshot will be taken with regard to this cut-off date; it will include all data available in the database up to and including the cut-off date and will be used for performing the analysis. Only cumulative results will be presented, i.e., patient level data will be excluded. Details regarding statistical analysis will be outlined in the TSAP. Only a selected team, not involved in any other trial activities, will have access to the unblinded snapshot data and will be required to sign a confidentiality agreement. Efficacy data will be included up to the Week 4 visit only and all available data for safety and other endpoints will be included up to the data cut-off date.

To ensure that the data integrity of the continuing trial will not be violated, a charter will be prepared in advance, outlining the procedures to be followed. This document will describe the measures to be implemented by the Sponsor to protect the integrity of the trial until the final database lock. Team members involved in the conduct of the trial as well as the site personnel and patients will remain blinded until the final database lock.

7.4.2 Final analysis

A final analysis (including all endpoints) will be performed when all trial data are available, i.e., approximately 56 weeks after the last patient has been randomized. In this analysis, all analyses performed for the primary analysis will be repeated with the (partially) updated data, in particular with respect to safety and efficacy endpoints collected until Week 56. The results of the final analysis will be summarized in a CTR.

7.5 HANDLING OF MISSING DATA

7.5.1 Efficacy endpoints

No missing data for the primary analysis endpoint are expected for the FAS, because Week 4 is the first post-baseline visit for efficacy assessment and, in case of discontinuation prior to Week 4, the EoT efficacy assessments should be performed. However, all patients who

discontinue treatment, are lost-to-follow-up or have any major protocol deviation related to any therapy that may significantly impact efficacy assessment (Table 4.2.2.1: 1) prior to the primary endpoint assessment will be considered as non-responders. Patients without any available CDAI evaluation at Week 4 will also be considered as non-responders. This is referred to as 'NRI'. Patients assessed as non-responders at Week 4 will be considered non-responders for all subsequent time points (LOCF).

For secondary efficacy endpoints, rules for handling of missing data will be specified in the TSAP, if necessary.

7.5.2 Safety and other endpoints

With respect to safety evaluations, it is not planned to impute missing values. For other endpoints, rules for handling of missing data will be specified in the TSAP, if necessary.

